6.3 Post Randomization Period

See Appendix 2 flowchart for designation of all study related procedures (standard of care and/or research purposes only)

6.3.1 Procedures for Day 0 baseline

6.3.1.1 Pre CYT107 administration

- History and Physical examination and lymphoid system examination
- Blood Sampling for : ALC count, Baseline PK and Immunogenicity assays

6.3.1.2 Post CYT107 administration Day 1 Week 1

- At 1, 3, 5, 7 and 9 hrs post treatment : Blood sampling for CYT107 PK assays (approximately 7 mL blood/timepoint from IV line)
- At 3 hrs post treatment :
 - Vital signs (Temperature, RR, Pulse and BP)
 - Review and record adverse events experienced
 - 12-lead electrocardiogram (ECG) and interpretation
- At 24 hrs post treatment (Day 2) : Blood sample for PK assay (total blood for PK over 24 hrs approx. 49mL)

6.3.2 Procedure for Days 4, 8, 15, 22, 29, 42

- APACHE II score, SOFA score, GLASGOW coma scale
- Physical examination and lymphoid system examination.
- Cardiac check: presence of vasopressors, EKG, MAP, HR,
- Respiratory check: PaO₂, FiO₂ (A-a Grad if FiO₂ ≥ 0.5 and patient on mechanical ventilation)
- Kidney functions: Creatinine, Urine analysis
- Liver function: ALT, AST, Bilirubin
- Sampling for:
 - Hematology (ALC, WBC, ANC, Mono, Platelets) and blood chemistry (including CRP, PT, PTT) as described in the flow chart,
 - PBMC for phenotyping and functionality test (CD3, CD4, CD8 T cells, HLA-DR expression, whole blood TNF- α as described in flow chart,

6.3.2.1 Additional procedure for day 11

- Blood sample for Immunogenicity assay

6.3.2.2 Additional procedure for day 22

- Before administration : Baseline blood sample for PK assay and Immunogenicity assay
- At 1, 3, 5, 7 and 9 hrs post treatment : Blood sampling for CYT107 PK assays
- At 3 hrs post treatment :
 - Vital signs (Temperature, RR, Pulse and BP)
 - 12-lead electrocardiogram (EKG) and interpretation
- At 24 hrs post treatment (Day 23) : Blood sample for PK assay (total blood for PK over 24 hrs approx. 49 mL)

6.3.2.3 Additional Procedure for Day 42

(See Appendix 2 Flow Chart for complete lists of clinical and laboratory studies.)

- ALC
- Hematology labs

6.4 Procedure for Days 60, 90, 180 and One Year Follow-up Period

Patients will be followed for 60, 90, 180 and 365 day outcomes regarding disposition, i.e., incidence of new secondary infections, long term status, i.e., still hospitalized, discharged to long term care facility or nursing home, discharged to home, and mortality.

Systematic blood sample for Immunogenicity testing at D60, repeated at day 180 and 360 if not negative for anti-CYT107 antibodies.

7.0 Safety and Biological Assessments

7.1 Clinical Safety

The following assessments will be performed on specified days (see flowchart) prior, during, and following therapy:

- Complete medical history obtained from the electronic medical record which should include
 - Past relevant medical and surgical history whether or not related to Sepsis
 - A complete Sepsis diagnosis and treatment history including actual or estimated start and stop dates of anti-sepsis treatments, and a complete history of any

prescription medications taken for the treatment of secondary opportunistic infections including start and stop dates and dose regimens

- All home prescription and non-prescription medications and dietary supplements will be recorded. All new medications within the last 3 weeks will also be recorded.
- Full physical examination including vital signs (temperature, pulse, resting blood pressure and respiratory rate), weight, and particular attention to the CYT107 injection sites.
- Reporting of AEs to the DSMB through-out study participation according to the “Division of AIDS table for grading the severity of adult and pediatric Adverse Events, Version 2.0, November, 2014”. Note that we are using the NIAID AIDS table for grading adverse effects because CYT107 (like IL-2) has been used in several clinical trials of AIDS patients and its potential adverse effects are well described and included in this table.
- ECG and Ultrasound

The following will be performed during the study according to the schedule described in Appendix II.

- ECG 12-lead with detailed analysis at screening, three hours after the first dose of CYT107 at Day 1 and three hours after CYT107 administration at approximately Day 22.
- Spleen ultrasound (3 dimensions): will be performed at screening, and at approximately D42. Laboratory Investigations per protocol (appendix 2).

7.1.1 Hematology and biochemistry (See Appendix 2 flow chart)

Hematology includes:

hemoglobin, hematocrit, red blood cells, mean corpuscular volume, white blood cells with differential (including ALC, platelets, Monocytes, Absolute Neutrophil Counts) Coagulation and inflammation markers: Prothrombin Time (PT), Partial Thromboplastin Time (PTT).

Chemistry includes:

Electrolytes (sodium, potassium, chloride, bicarbonate, calcium, magnesium and phosphorus), creatinine, glucose, albumin, liver function tests (total bilirubin, AST, ALT, Alkaline Phosphatase), and CRP (C-reactive protein).

7.2 CYT107 Pharmacokinetics

Pharmacokinetic profile will be determined in all patients.

Samples will be collected at D1 and D22 at pre-dose (0) and at approx:

1, 3, 5, 7, 9 and 24 hrs post dose

Samples will be analyzed for CYT107 content and data analyzed to determine the main PK parameters: C_{max}, T_{max}, AUC, half-life.

7.3 CYT107 Immunogenicity

Specific CYT107 binding and neutralizing antibody studies will be performed.

Samples will be collected at D1, D11, D22, and at approximately D60.

If the D60 binding antibodies test is positive, samples will be tested for the presence of neutralizing antibodies. Another sample will be tested for binding antibodies at approximately day 180. The same will be done at approximately D360 if D180 is positive.

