
Objectives
	
Primary Objective To study the biological activity and safety of two dosing regimens of CYT107 at 10 µg/kg twice a week for the first week, followed by:
 
 • Once a week for the low frequency regimen • Twice a week for the high frequency regimen • Control group: will receive placebo (NaCl 0.9%) twice a week 
Activity The primary objective is to demonstrate that treatment of lymphopenic septic patients with CYT107 will reverse their low absolute lymphocyte count (ALC) which is a marker of immunosuppression and which correlates with mortality. This primary end point, increased, ALC by >50% in septic patients with lymphopenia, will be measured in the control (placebo) and two “dosing frequency” groups at approximately day 42 following randomization and initiation of study drug treatment.
 
Safety To characterize the short term safety in a context of a single cycle of CYT107 (4 weeks) administered according to these two dosing regimens in lymphopenic sepsis patients. Based on the data collected from previous CYT107 studies in Oncology and HIV infection,(12)(13)(14)(15) treatment of lymphopenic sepsis patients with CYT107 is expected to increase the absolute lymphocyte count (ALC) by greater than 50% from baseline by day 42 after therapy is initiated.
 
To date, CYT107 has not been tested in patients with sepsis. Septic patients frequently have decreased kidney and liver function, changes in circulating blood volume, and loss of vascular integrity with leakage of proteins into the interstitial space.(2) These alterations might impact the pharmacokinetics and pharmacodynamics of CYT107. Thus, we will administer CYT107 using a protocol that is highly similar to a previous protocol that was effective in improving the ALC in patients with cancer, HIV, and hepatitis C and was well tolerated with a low incidence of serious adverse effects.(12)(13)(14)(15)(17).
 
The incidence, type and severity of adverse events occurring during the 6 weeks study period will be analyzed for the control arm and two “dosing frequency” groups.
 
Secondary Objectives To characterize CYT107 pharmacokinetics (PK) in patients with sepsis To characterize CYT107 immunogenicity by detection and quantification of binding antibodies and detection of neutralizing antibodies in positive samples To characterize CTY107 pharmacodynamics, specifically to determine if CYT107 can restore depressed functional activity of immune effector cells in patients with sepsis To determine if CYT107 decreases the incidence of secondary infections in septic patients

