
Secondary Biological Activity Study Endpoints
	
1) To determine pharmacokinetics (PK) including Cmax, area under the curve,(AUC) and T^{1/2} life of CYT107 in patients with severe sepsis and multiple organ failure who are treated with 10 µgs/kg ideal body weight using 2 different dosing regimens
 
2) Assessment of CYT107 immunogenicity by detection and quantification of binding antibodies and detection of neutralizing antibodies in positive samples
 
3) To determine pharmacodynamics (PD) including effects of CYT107 therapy to:
 
 i) improve absolute numbers and function of immune effector cells ii) changes in the absolute numbers of CD4+ and CD8+ T cells over the study period, standardized on the duration in the study. iii) Changes in the expression of the CYT107 receptor (CD127) on the surface of CD4+ and CD8+ T cells. iv) Effects of CYT107 on circulating monocyte HLA-DR expression v) Effects of CYT107 on whole blood LPS-stimulated TNF-α vi) Effects of CYT107 on anti-CD3/anti-CD28 stimulated peripheral blood mononuclear cells to produce IFN-γ. 
4) To determine effect of CYT107 to decrease the incidence of secondary infections. CYT107 has been highly effective in clinically relevant bacterial and fungal animal models of sepsis.(16)(18) We will compare the effect of CYT107 to reduce hospital-acquired secondary infections in CYT107 treated septic patients versus a control group of septic patients who receive placebo. The rate of hospital-acquired secondary infections at 42 days is roughly 35-40%.(20) We speculate that CYT107 will reduce the rate of secondary infections from 35-40% % to 25%.

---	--

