2.5 Risk-Benefit Ratio

Sepsis causes extensive apoptotic death of immune effector cells leading to an impaired immune system. CYT107 prevents sepsis induced cell death and improves survival in many clinically-relevant animal models of sepsis. We postulate that by improving host immunity, CYT107 will improve the ability of septic patients to eradicate their primary infection and decrease the incidence of new secondary infections. Given the low risk of adverse effects in patients treated with CYT107 and the potential for benefit, we believe that the risk benefit ratio lies greatly toward use of CYT107 in patients who have a highly likelihood of dying from sepsis; the expected mortality in septic patients who meet the entry criteria for this CYT107 study is approximately 45% at 60 days.

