schematic "preliminary study" design																																																		
	Week 1							Week 2							Week 3							Week 4					Week 5				Week 6																			
days	1	2	3	4	5	6	7	8	9	10	11	12	13	14	15	16	17	18	19	20	21	22	23	24	25	...	28	29	...	35	36	...	42																	
IL-7	X			X				X			X				X			X				X			X																									
	X			X				X			P				X			P				X			P																									
PBO	P			P				P			P				P			P				P			P																									
ALC	X			X				X			X				X			X				X			X			X					X												X					
	TREATMENT																												FOLLOW UP																					
	IL-7 admin in 10 patients "high frequency dosing"																																																	
	IL-7 admin in 10 patients "low frequency dosing"																																																	
	10 Placebo Controls																					determination of ALC recovery and IL-7 clinical tolerance																												
	Absolute Lympho Counts																																																	

Dosing regimen for CYT107 in septic patients showed administration details of the “high frequency dosing” – (shown in red color) or the low frequency dosing (shown in blue color). The ALC is quantitated weekly throughout 6 weeks duration. Given that CYT107 will boost host immunity, we predict that patients treated with CYT107 will have decreased incidence of new secondary infection, decreased hospital readmissions (which generally are due to new secondary infections), and improved 60 day, 90 day, 180 days and one year mortality. Thus, these parameters will be recorded in all patients. The 60 day, 90 day, and one year data will be obtained by telephone interview, physician records, or by interrogating appropriate databases and newspaper obituary records. The patients will not have to be seen in clinic.

Additional experimental details:

- Patients with severe sepsis and organ failure who are admitted to the ICU are candidates. Septic patients who are not being treated in the ICU are not candidates for study enrollment.
- Septic patients will continue to receive the CYT107 to complete the full dose schedule even if their sepsis has resolved if they remain in the acute care hospital setting. Patients will not receive additional doses of CYT107 if they are discharged from the hospital.

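### Section 7.3 triggers neutralising-antibody testing only from a positive day-60 binding test, which is narrower than the endpoint and depends on surviving to, and being sampled at, day 60

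*Protocol*

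**What the plan says.** The Synopsis lists as a secondary objective "To characterize CYT107 immunogenicity by detection and quantification of binding antibodies and detection of neutralizing antibodies in positive samples". The matching endpoint, in the Synopsis and again in Section 4.3.2, is "Assessment of CYT107 immunogenicity by detection and quantification of binding antibodies and detection of neutralizing antibodies in positive samples". None of these statements names a visit.

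Section 7.3 opens generally: "Specific CYT107 binding and neutralizing antibody studies will be performed". It then sets the schedule, "Samples will be collected at D1, D11, D22, and at approximately D60", and gives one trigger for the second assay: "If the D60 binding antibodies test is positive, samples will be tested for the presence of neutralizing antibodies". It goes on to later binding tests at about days 180 and 360. It has no rule for a positive day-11 or day-22 sample, or for a patient without a day-60 sample.

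Other sections bear on this:

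- Section 6.3 repeats the baseline, day-11 and pre-dose day-22 immunogenicity samples.
- Section 6.4 makes the day-60 blood sample systematic.
- The text under Figure 8 in Section 4.2 says that 60-day and later data come by telephone, records or databases, and adds "The patients will not have to be seen in clinic".
- Section 8.6.2 allows an immunogenicity sample at the last visit after early discontinuation, with no rule for neutralising tests on it.
- Section 2.5 expects mortality of "approximately 45% at 60 days"; Section 14.2 gives 40-45% at 60-90 days.
- The SAP does not mention immunogenicity.

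**The concern.** The endpoint attaches the neutralising test to a positive sample. Section 7.3 attaches it to a positive result at one late visit, 35 days after the last scheduled injection (day 60 minus day 25). In a population with high expected mortality, that visit is reached by a selected group. A laboratory working from Section 7.3 would have no instruction to run the assay for a patient who was positive during treatment and then died, was not sampled, or had turned negative.

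Immunogenicity influenced the design. Sections 2.4.3.1 and 3.2.1 give it as a reason to prefer the intramuscular route, while patients with coagulopathy receive the drug subcutaneously. PK is repeated on day 22 and ALC is followed to day 42. Knowing whether antibodies present on day 11 or 22 were neutralising could help to explain altered exposure or a weak ALC response. Under the stated trigger that information exists only for patients who are also positive at day 60.

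**Working it through.** The documents give no sample size, power or expected rate for immunogenicity, so there is no stated figure to reproduce. The check has two parts.

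**1. The rule against the endpoint**

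| Patient's binding results | Endpoint (Synopsis, 4.3.2) | Section 7.3 read literally |
|---|---|---|
| Positive at day 60 | Neutralising test | Neutralising test |
| Positive at day 11 or 22, negative at day 60 | Neutralising test | No route stated |
| Positive at day 11 or 22, no day-60 sample (death or missed) | Neutralising test | No route stated |
| Positive in the early-discontinuation sample, no day-60 sample | Neutralising test | No route stated |

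The plural in Section 7.3 might mean that stored earlier samples are tested too. That helps only the first row, because a day-60 positive is still needed.

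**2. How many patients could fall outside the trigger**

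Inputs: 20 CYT107 patients, 10 per regimen (Section 4.2); mortality p = 0.40 or 0.45 by day 60 (Sections 2.5 and 14.2); patients who do not complete two weeks are replaced (Sections 4.2, 6.2 and 11.1).

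*Before replacement*, expected deaths = 20 × p:

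- p = 0.40: 20 × 0.40 = 8 (95% binomial range 4 to 12)
- p = 0.45: 20 × 0.45 = 9 (range 5 to 13)

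So 11-12 of 20 can reach the trigger if every survivor is sampled. If 80% of survivors give a day-60 sample (assumption), it is 12 × 0.8 = 9.6 or 11 × 0.8 = 8.8, leaving 10.4 to 11.2 of 20 with no day-60 result.

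*After replacement*, let f be the share of day-60 deaths that fall before day 14. The documents do not give f; 25% and 50% are assumptions. Mortality from day 14 to day 60 among those alive at day 14 is q = p(1 − f)/(1 − pf):

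| f | p = 0.40 | p = 0.45 |
|---|---|---|
| 0.25 | 0.300/0.900 = 0.333, so 6.7 of 20 | 0.3375/0.8875 = 0.380, so 7.6 of 20 |
| 0.50 | 0.200/0.800 = 0.250, so 5.0 of 20 | 0.225/0.775 = 0.290, so 5.8 of 20 |

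About 5-8 of 20 evaluable CYT107 patients would therefore die between days 14 and 60.

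These are counts of patients without a day-60 sample because of death. They do not count lost positives. That number also needs the day-11 and day-22 binding-positive rate and the rate of reversion by day 60, and the documents give neither.

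**The case against.** The strongest reply is that this is loose wording. Section 7.3 does not say that day 60 is the sole trigger. Its opening sentence plans both kinds of antibody study, and the objective and both endpoint statements refer to "detection and quantification of binding antibodies and detection of neutralizing antibodies in positive samples". The trigger sentence could be read as part of the follow-up sequence from day 60 to days 180 and 360. A sponsor could say that any positive sample was always going to be tested. That may be the intention, but no other trigger is written, and neither Section 8.6.2 nor the SAP supplies one.

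Other parts of the reply stand, and they rule out stronger readings that a reader might infer:

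- *That antibodies during treatment go unseen.* Binding antibodies are sampled on days 11 and 22. Only their neutralising capacity may be missed.
- *That untested patients count as negative, so incidence is biased towards zero.* No counting rule or denominator is given. Section 9.2.4 promises only descriptive and simple inferential analyses. Untested patients could equally be shown as missing.
- *That no day-60 sample is planned for discharged survivors.* Section 6.4 orders one. The Section 4.2 statement concerns outcome data, so the two passages conflict; the sample is not absent.
- *That 9 of 20 evaluable patients lack a day-60 sample through death.* Deaths before two weeks are replaced and do not come out of the evaluable 20. Those replaced patients were still dosed, and they belong to the safety set in Section 9.2.1.2.
- *That the change gains the precision of 20 patients over 11* (upper exact limits with no events of 16.8% against 28.5%). This assumes that every patient is recovered. A patient who dies before day 11 has no scheduled post-dose sample.

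**Conclusion.** The point stands as a mismatch between a stated rule and the endpoint it serves. The only written trigger is a positive day-60 binding test, so neutralising-antibody assessment is incomplete and conditional on survival, sampling and persistent positivity at day 60.

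It would go too far to say that the immunogenicity objective is missed. The binding part is unaffected, and the neutralising part can still be met for day-60 positives. The endpoint is secondary and descriptive, and the primary ALC analysis is untouched. The change is worth making because it is easy and the exposed group is not small.

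The sizes in the working rest on the Protocol's own mortality figures and, for the evaluable patients, on an assumed timing of deaths. Missed day-60 samples among survivors would add to them. The Appendix 2 flow chart is not in the available text and may list further sampling or testing.

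**What to change.** 1. Amend Section 7.3 so that any binding-positive post-dose sample is tested for neutralising antibodies: day 11, day 22, day 60, or the early-discontinuation sample in Section 8.6.2. Day 60 stays as the late time point.
2. State in the SAP that incidence is reported over dosed patients with at least one post-dose sample, and that patients with none are shown as missing, not as negative.
3. Reconcile the no-clinic-visit statement in Section 4.2 with the systematic day-60 blood sample in Section 6.4, so that sites know how the sample is obtained from discharged patients.

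The cost is a few extra assays, on samples that the Protocol already plans or allows. The change cannot recover patients who die before their first post-dose sample.

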7.4 CYT107 Pharmacodynamics/Immunology

The immune monitoring will include:

Differential count of T cells CD3, CD4, CD8

Monocyte HLA-DR expression

Whole blood TNF- α production

8.0 Investigational Medicinal Product (see details in Investigator's Brochure)

8.1 CYT107

8.1.1 Description

CYT107 (CYT107) is a recombinant protein belonging to the class of growth factors and more specifically to the class of cytokines. CYT107 is a heavily glycosylated and sialylated form of recombinant human interleukin-7 expressed from a CHO cell line, composed of 152 amino acids, with an average molecular mass as determined by mass spectrometry of 22 kDa and a mean pI of 7. The molecular formula of the peptidic sequence only (non glycosylated) is C₇₆₂H₁₂₄₁N₂₁₃O₂₂₈S₁₁. The protein contains 3 disulfide bridges (Cys2- Cys 92, Cys 34- Cys 129, and Cys 47- Cys 141) and 4 glycosylation sites (3N, 1O).

8.1.2 Source

CYT107 used in this clinical trial was manufactured under good manufacturing practice (GMP) criteria at a 600 L fermentation and purification scale by PATHEON (Princeton, NJ), for REVIMMUNE Inc. At clinical site, the product will be made available to the hospital pharmacy by CSM, Fargo, ND58103.

8.1.3 Formulation

CYT107 is supplied in a 2 mL vial as 0.5 mL of CYT107 (1 mg) in 10 mM Sodium Acetate, 100 mM NaCl, 50 mM glutamic acid. The pH of the solution is 5 and the osmolality is 320 \pm 40 mOsm. The concentration of CYT107 in solution is 2 mg/ml.

8.1.4 Stability

Stability studies will continue throughout the clinical study. Updated stability information will be periodically communicated to the hospital pharmacy.

8.1.5 Special Handling

There are no specific guidelines for safe handling of CYT107. Institutional guidelines for safe handling of proteins in general should be followed.

8.1.6 CYT107 Preparation

Syringes containing the CYT107 dose (placebo dose same volume of NaCl 0.9%) will be prepared by the hospital pharmacy and delivered to the clinic in a blinded fashion. The product

should be defrosted at least 1 hour before administration. Defrosted product (and possibly put in syringe) should be kept refrigerated at +4°C/+8°C until use and for no more than 12 hours.

CYT107 ampoule will only be used if the solution is clear (following visual inspection), the vial is undamaged and the use by (expiration) date (if marked on the vial) has not been passed.

Based on patient's ideal body weight on day of study entry, the appropriate number of vials of CYT107 drug product will be prepared and administered. CYT107 will be kept refrigerated until time of immediate administration to the patient. To minimize the chance for contamination, sterile or septic technique should be carefully observed during CYT107 solution preparation (filling of the syringe) and administration.

A vial is restricted for use by a single patient. Take no more than 0.5 mL into the syringe. The dose to be injected will be divided as necessary into multiple intramuscular injections so that each injection will not exceed 0.5 ml in volume. (Dosing guidelines for ideal body weight make the requirement for multiple injections highly unlikely).

